5. STUDY TREATMENTS

5.1. Treatment Assignment

Subjects will be randomly allocated in a two to one ratio to receive treatment or placebo. Subjects and investigators will be blinded to randomization. Randomization will be stratified according to splenectomy status. Randomization will be performed at the time of informed consent with a computer generated randomization table

5.2. Product Accountability

Product will be dispensed from Investigational Pharmacy to investigators and study coordinators for distribution to subjects.

5.3. Treatment Compliance

Subjects will bring in used medication vials at each study visit for review and medication compliance will be assessed.

5.4. Concomitant Medications and Non-Drug Therapies

5.4.1. Permitted Medications and Non-Drug Therapies

Subjects will be allowed to continue with concomitant non-ITP medications, but will be excluded from analysis as described (for the subsequent 2 weeks) if rescue therapy for treatment of ITP is needed during the duration of the study.

A subject whose platelet count is > 50,000/ μ l can receive aspirin or Plavix or warfarin at the discretion of the investigator.

5.5. Treatment after the End of the Study

As described for cross-over of placebo patient after unblinding and long term extension phase of study.

5.6. Treatment of Investigational Product Overdose

Treatment of any suspected or confirmed overdose with eltrombopag should be symptomatic with supportive care as dictated by good clinical practice. There is no known antidote for eltrombopag, although antacids can be considered to limit the absorption of eltrombopag.

5.7. Treatment Plan

| Bodily Fluid | Amount | Frequency | Total |
|--------------|--------|-----------|-------|
|--------------|--------|-----------|-------|

| | | | |
|------------------------|----------------------------------------------------------------------|------------------------------------------------------------------------------------------------------------------------------------------|----------------------------------|
| Blood | 10-80cc As needed amounts will be adjusted for pediatric subjects | Bi-weekly for 8 weeks, in 4 week intervals, then every 8 weeks (visits at the discretion of the investigator) | > 400 cc |
| Bone Marrow Aspiration | 10 cc | 1 time (after 12 +2 months of study medication during Part 2 of the study) unless bone marrow fibrosis grade is a 2 or 3 (then annually) | 10 cc per bone marrow aspiration |
| Urine | 5- 10 cc | 1 time | 5-10 cc |

STUDY ASSESSMENTS AND PROCEDURES

Table 1 See Appendix 1

6.1. Critical Baseline Assessments

Screening to ensure subject eligibility criteria will occur within 30 days prior to administration of study medication. Screening assessments will include CBC, CMP (Sodium, Potassium, Bicarbonate, Chloride, BUN, Creatinine, Glucose, Calcium, Total Protein, Albumin, including AST/ALT, Fractionated Bilirubin Level), D-Dimer and urine pregnancy test (for women of childbearing potential).

6.2. If subject meet all other criteria for enrollment, a baseline ophthalmologic examination will be performed within 2 weeks of administration of study medication.

6.3. Primary Response Criteria:

Complete Response (CR) will be defined as a 2 consecutive platelet counts $\geq 50,000 / \mu\text{L}$ AND $> 20,000$ more than the baseline platelet count at enrollment within the 8 week increased dose window not as a result of rescue treatment. Partial Response (PR) will be defined as a 2 consecutive platelet counts $\geq 50,000 / \mu\text{L}$ OR $> 20,000$ more than the baseline platelet count at enrollment within the 8 week increased dose window not as a result of rescue treatment.

For uniformity of dosing and data analysis and for better understanding of increased dose effects, patients randomized to the treatment arm will automatically take:

- 100 mg for 2 weeks
- 125 mg for 2 weeks
- 150 mg for 4 weeks

However, if the platelet count increases to $\geq 100,000 / \mu\text{L}$, study drug will be interrupted and will not be resumed until platelet count is below 100,000 / μL and the patient desires to enroll on the Part 2 long term treatment extension study. The patient will finish with the Part 1 of the study at this point but can enter Part 2 the long term treatment extension study at dose at which the patient met primary response criteria, after the platelet count decreases to $< 100,000 / \mu\text{L}$ on serial immediate post-study monitoring period.

Rescue treatment will be defined as new treatment for chronic ITP eg IV anti-D or IVIG, an increased dose of steroids, or platelet transfusion. Use of rescue treatments will be allowed, but patients will be regarded as non-responders for the duration of rescue treatment and until 2 weeks beyond.

Secondary Response Criteria:

-Platelet Count $\geq 50,000$ and $> 20,000$ above baseline for at least 3 of the last 4 of 8 weeks independent of rescue therapy

- Platelet Count \geq 50,000 /uL and $>$ 20,000 above baseline for any 4 of 8 weeks independent of rescue therapy
- At least One Platelet count \geq 100,000
- Number of weeks with Platelet Counts \geq 50,000 /uL and $>$ 20 from baseline in 8 Weeks reduction of bleeding score from baseline to the last count of the study improvement of HRQoL
- Number of weeks with Platelet Counts $>$ 100,000 in 8 Weeks

Secondary Efficacy Endpoints:

- Dose required achieving first platelet count \geq 50,000 /uL and $>$ 20 from baseline
- Average Platelet Count at each dose level
- Bleeding scores using WHO score
- Use of Rescue Treatments

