2. OBJECTIVE(S)

2.1. Primary Objective

To determine the proportion of patients with chronic ITP who do not respond to 75 mg of eltrombopag daily given for at least 3 weeks but then do respond to eltrombopag given daily first for 2 weeks at doses of 100, then for 2 weeks at 125 mg and finally for 4 weeks at a dose of 150mg daily. The intial double-blind phase will stop if/when the platelet count exceeds 100,000/uL. Complete response (CR) will be defined as 2 consecutive platelet counts of greater than or equal to 50,000 AND an increase of greater than or equal to 20,000 from the study baseline within the 8 week increased dose window not as a result of rescue treatment. Partial response (PR) will be defined as 2 consecutive platelet counts of greater than or equal to 50,000 OR an increase of greater than or equal to 20,000 from the study baseline within the 8 week increased dose window not as a result of rescue treatment.

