3. INVESTIGATIONAL PLAN

3.1. Study Design

Double-blind, randomized, placebo-controlled trial in subjects with ITP who are 'non-responders' at the maximum package insert dose (75mg) of eltrombopag; non-responders are those with platelet counts $< 50,000$ despite taking 75 mg/day of eltrombopag for at least 3 weeks.

Study Design (First part): 8 Weeks

Informed consent and assent of minors will be obtained by the principal investigators or sub-investigators. Typically, informed consent/minor assent will be obtained in the outpatient clinic, although inpatients may have this discussed with them as well. Consent will be obtained after review of clinical information and satisfaction of eligibility criteria. Subjects will be randomly allocated at a two to one ratio to receive active treatment or placebo. All subjects must be ≥ 3 years old and able to swallow a tablet. in the study will receive 75 mg eltrombopag and then be randomized to receive either an additional 25 mg of eltrombopag or matching placebo tablet dispensed by the research pharmacy

Subjects and investigators will be blinded to randomization. Randomization will be stratified according to splenectomy status. Randomization will be performed at the time of informed consent with a computer generated randomization table as per the pharmacy. Subjects may enroll and begin taking 75 mg eltrombopag for at least 3 weeks. When subject's platelet count is $< 50,000$, the subject may begin day 1 of the study. Subjects and investigators will be blinded to assignment and treatment in this phase. Eltrombopag will be administered for 8 weeks or until the platelet count exceeds 100,000; at this point dosing will stop, subject will be considered a responder and the subject will eligible for entering Part 2 (the long term treatment part of the study) if desired and agreed to be appropriate by the subject giving consent, and the treating physician. The dose at which the subject achieved the primary endpoint ($> 50,000$ and increase by $> 20,000$) will be considered the dose of response. Even if a patient achieves a response, if the platelet counts remains $< 100,000$, then the dose escalation schema in the figure above will continue.

[figure not shown]

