Dose escalation will continue, despite satisfaction of the primary endpoint of study ($> 50,000$ and $> 20,000$ above baseline), until the platelet count reaches 100,000. The rationale for this approach is to maximize clinically relevant responses for the subjects and standardize data for analysis. Subjects will stop study medication if the platelet count is within the normal range, thereby minimizing any safety risk associated with elevated platelet count. By continuing to dose escalate subjects until the platelet count is $> 100,000$, the maximum response and correlation of dose will be tracked allowing better understanding of sustained response and dose-dependent response, which can be applied to future consideration dosage for periods of short-term hemostasis (i.e surgical procedures). The 8 weeks of data collected in enrolled subjects on the standardized

protocol will have the balance of consistency of dosage and unequivocality of response while maintaining subject safety.

If agreed on by the P-I, subjects may obtain local counts or see their local hematologist for study visits. All study-required procedures will be faxed to the P-I for review. The appropriate dosing adjustments will be determined by the P-I.

According to the new consensus guidelines (Provan Blood, 2009), male and female subjects with > 1 year duration of ITP are diagnosed with chronic ITP. Enrollment began with adult subjects \geq 18 years of age, and was extended to include pediatric patients $>$ 12 years of age after a review of this unblinded safety information by the independent Data Safety Monitoring Officer (DSMO). Additionally, we will now allow the inclusion of pediatric patients \geq 3 year of age to enroll on the protocol. The rationale for treating patients on this study is to allow people to be successfully treated and thus increase their platelet count by using a higher dose of eltrombopag when they do not respond to 75 mg daily of eltrombopag. Since some children do not respond to 75mg, the rationale and the dosing (when and how to increase) would be the same.

Long Term Treatment Extension (Part 2): (48 months)

After 8 weeks or once dosing is stopped because the platelet count is $>100,000$, the subject will be unblinded, once the data forms are complete with the assistance of the research pharmacy.

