The trial will have an 80% statistical power at the 5% level of significance (two sided) to detect a difference in the proportion of subjects receiving increased dose of eltrombopag with a primary response (2 consecutive platelet counts of > 50,000 and an increase of > 20,000 from the study baseline with in the 8 week increased dose window not as a result of rescue treatment) to subjects without a primary response in the placebo group assuming 50% of subjects randomized to active drug will have a response and 5% of subjects randomized to placebo would have a response. The same statistical test will be run for subjects who achieve partial response. An interim analysis was performed after 18 subjects to test for futility and efficacy.

Dose modification during the long term extension portion of the trial will be made on the basis of individual platelet response to a maximal dose of 150mg. All subjects can be monitored at 4 weeks intervals and then can go to every 8 weeks for the remainder of the study at the discretion of the investigator (investigator may require subjects to come in for additional monitoring if deemed necessary).

If the platelet count is > 150,000 ul and < 400,000 ul the daily dose will be adjusted and if > 400,000 ul the medication will be held and monitor will be as per the prescribing information for eltrombopag in the package insert. However, if the P-I determines that adjusting the subject's dose will negatively affect the subject, he or

she may decide not to escalate or reduce the subject's dose. Circumstances in which this may occur include, but are not limited to: investigator is tapering other medications or the subject has a viral infection. Viral infections have been known to both increase and decrease platelet count in patients with ITP. It is suggested that the increased presence of inflammatory molecules during a viral infection increases platelet production, causing platelet count to increase. Alternatively, platelet count may decrease by virtue of activating the reticuloendothelial system causing greater phagocytosis of antibody-coated platelets and/or platelet production.

Laboratory/Assessment Testing

Please see Appendix 1 for Schedule of Events.

Screening

CBC with Differential
Reticulocyte Count
Peripheral Smear
CMP (Sodium, Potassium, Bicarbonate, Chloride, BUN, Creatinine, Glucose, Calcium, Total Protein, Albumin, including AST/ALT, Fractionated Bilirubin Level)
Urine Pregnancy Test (when appropriate)

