8. DATA ANALYSIS AND STATISTICAL CONSIDERATIONS

8.1. Hypotheses

Subject who did not respond at a dose of 75mg daily, eltrombopag will respond with increasing platelet count to $> 50,000$ and $> 20,000$ above baseline at a higher daily dose of 100, 125 and 150mg.

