8.2. Study Design Considerations

8.2.1. Sample Size Assumptions

The trial will have a 80% statistical power at the 5% level of significance (two sided) to detect a difference in the proportion of patient receiving increased dose of eltrombopag with a primary response (Platelet Count $\geq 50,000$ per cubic millimetre and $> 20,000$ above baseline) to patients without a primary response in the placebo group. assuming 50% of patients randomized to active drug will have a response and 5% of patients

randomized to placebo would have a response. An interim analysis will be performed after 18 subjects to test for futility and efficacy and also to re-estimate sample size. If neither futility nor efficacy are met the trial would continue to enroll. Based on the observed treatment effect at the interim analysis the sample size would be allowed to expand to up to 60 subjects

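### The complete-response cut-off is written in three versions with none said to govern, and two descriptive secondary endpoints give the platelet rise as > 20 beside a level in /uL

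*Combined protocol and SAP*

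**What the plan says.** **Primary (complete) response.** The level and rise cut-offs appear in three forms.

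- **Version (a)**, section 2.1: "greater than or equal to 50,000 AND an increase of greater than or equal to 20,000 from the study baseline".
- **Version (b)**, both limits strict. Section 3.1 has it three times: in the dose-of-response sentence ("achieved the primary endpoint ($> 50,000$ and increase by $> 20,000"), in the dose-escalation rationale ("satisfaction of the primary endpoint of study ($> 50,000$ and $> 20,000$ above baseline") and in the power paragraph ("2 consecutive platelet counts of > 50,000 and an increase of > 20,000 from the study baseline"). The hypothesis in 8.1 also uses it: "increasing platelet count to $> 50,000$ and $> 20,000$ above baseline".
- **Version (c)**, level at least 50,000 and rise strictly above 20,000. It is in the Primary Response Criteria of 6.3 and 8.3.1.1 ("AND $> 20,000$ more than the baseline platelet count at enrollment") and in the sample size text of 8.2.1 ("per cubic millimetre and $> 20,000$ above baseline").

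Sections 2.1, 6.3 and 8.3.1.1 also define a partial response (PR) by joining the same two limits with OR. Section 3.1 says the same test will be run for PR but gives no PR limits of its own.

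**Secondary endpoints.** In both 6.3 and 8.3.1.1, the number of weeks of response and the dose at first response require a level of at least 50,000 /uL and a rise of > 20 with no unit. The first reads "and $>$ 20 from baseline in 8 Weeks". The first two Secondary Response Criteria in the same lists ask for a rise above 20,000.

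**The concern.** A binary primary endpoint needs one rule that a programmer can apply without choosing. Here the objective, the hypothesis and the two Primary Response Criteria sections give three rules, and the two power statements (3.1 and 8.2.1) disagree with each other on the level. If platelet counts are recorded in whole thousands, values of exactly 50,000 and rises of exactly 20,000 will occur, and the version chosen decides whether such a subject is a complete responder.

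The choice would now be made late. The interim analysis of 18 subjects has been done and reports complete response rates by sex. The documents do not state which cut-off it used. The Primary Response Criteria are printed under the interim heading in 8.3.1.1, but in the future tense and without saying that the interim results rest on them.

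The > 20 wording is a separate defect. Eligibility caps the platelet count at 50,000 /uL, so a literal rise of 20 platelets per uL leaves little more than the level test. It also gives the response dose two definitions, because 3.1 already defines it with a rise above 20,000.

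**Working it through.** **1. The plan's sample size.** Inputs from 8.2.1 and 5.1: 50% active, 5% placebo, two-sided 5%, 80% power, 2:1 allocation. Using a normal approximation with pooled variance and no continuity correction:

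- Pooled rate = (0.05 + 2 × 0.50)/3 = 0.35.
- Placebo n = [1.96 √(0.35 × 0.65 × 1.5) + 0.842 √(0.05 × 0.95 + 0.50 × 0.50/2)]² / 0.45² = (1.1449 + 0.3496)² / 0.2025 = 11.03, rounded up to 12.
- Active n = 24, total 36, matching the 36 in 8.3.1. Power at 24 v 12 is 84.1% (normal approximation) or 81.5% (exact Fisher).

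The cut-offs do not enter this formula; only the assumed rates do. The conflict therefore leaves 36 unchanged.

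**2. Classification, with two consecutive equal counts (thousands per uL).**

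| Baseline → counts | (a) 2.1 | (b) 3.1, 8.1 | (c) 6.3, 8.3.1.1 |
|---|---|---|---|
| 30 → 50 | CR | not CR | PR, not CR (rise is exactly 20) |
| 35 → 55 | CR | not CR | PR, not CR |
| 20 → 50 | CR | not CR (level is exactly 50) | CR |
| 45 → 52 | PR, not CR | not CR | PR, not CR |

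**3. When the rise limit matters.** A count of at least 50,000 from baseline b is a rise of at least 50,000 − b.

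- A rise of at least 20,000 is automatic for b ≤ 30,000.
- A rise above 20,000 is automatic for b < 30,000.
- A rise above 20 per uL is automatic for b < 49,980, so it filters almost nobody. The 45 → 52 subject, who is not a CR under any version, would count as responding in both secondary endpoints.

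**4. Size for the primary endpoint.** The documents give no distribution of counts, so this is an assumption: lognormal counts rounded to whole thousands, entry at or below 50,000, median 25,000, within-subject log SD 0.3 to 0.6, one baseline and four Part 1 counts.

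- No drug effect: the loosest and strictest versions differ by 0.3 to 0.5 points. In a placebo arm of 12 to 20 (one third of 36 to 60), that is 0.003 × 12 = 0.04 to 0.005 × 20 = 0.10 of a subject.
- About 45% to 49% responding: 1.1 to 1.6 points, that is 0.011 × 24 = 0.26 to 0.016 × 40 = 0.64 of a subject in an active arm of 24 to 40.
- Unrounded counts (within-subject log SD 0.45): the three versions give identical rates.

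**5. What one subject can do.** One reclassified subject moves the rate by 1/24 = 4.2 points in the active arm or 1/12 = 8.3 points in the placebo arm. Two-sided Fisher tests, as illustration: 10/24 v 0/12 gives p = 0.015; 10/24 v 1/12 gives p = 0.059.

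**6. Size of the literal > 20 reading.** Under the same assumptions and no drug effect, subjects with at least one qualifying count rise from 10.0% to 15.5% (log SD 0.3), 20.9% to 25.1% (0.45) and 30.7% to 33.9% (0.6). These figures apply only if someone programs 20 platelets per uL.

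**The case against.** The strongest reply is that this is editorial. At least versus more than matters only for exact ties, and with unrounded counts the versions agree. By the figures above, the expected shift in the placebo arm is a tenth of a subject or less. The > 20 sits directly below criteria that say > 20,000, and 6.4 elsewhere writes counts as ×10^9/L, where 20 is the same quantity. Few analysts would code it literally. It affects only secondary analyses, which 8.3.1 calls underpowered and descriptive. All of that stands, and it limits the weight of the point. It does not settle which version governs.

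Three stronger readings are tempting, and the documents do not support them.

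- **That the 30,000-to-50,000 subject is a non-responder in 6.3 and 8.3.1.1.** Two counts of 50,000 meet the level limit of the PR definition there, so the subject is a PR. The disagreement is CR versus PR.
- **That the > 20 wording dilutes the active–placebo contrast.** The simulation in step 6 covers only the no-effect case, so it shows no contrast, and no confirmatory comparison uses these endpoints.
- **That the sample size is wrong.** It reproduces.

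Nor should the Fisher example be read as a likely outcome. At 12/24 v 0/12 or 1/12, the p-values are 0.003 and 0.025, and the conclusion does not change.

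**Conclusion.** The point holds as an inconsistency in decision thresholds that should be corrected. Three versions of the primary cut-off coexist, none is said to govern, and the same subject can be a CR in one section and not in another. The average effect is small: 0.3 to 0.5 points with no drug effect and 1 to 2 points near 45% response, assuming lognormal counts in whole thousands. The number of subjects actually on a boundary is not given. It still deserves fixing because a single placebo reclassification can carry a borderline result across 5%, and because a cut-off chosen after an interim look is open to the charge of being data-driven.

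The > 20 rise is wrong as written, most likely a dropped ',000' or unit. Its reach is confined to two descriptive secondary endpoints.

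**What to change.** 1. For the analysis, use one primary definition in 2.1, 3.1 (all three places), 6.3, 8.1, 8.2.1 and 8.3.1.1. At least 50,000 /uL and more than 20,000 /uL above baseline is the natural choice, since both Primary Response Criteria sections and 8.2.1 already use it. Apply the same limits to PR.
2. In 6.3 and 8.3.1.1, change the rise in both secondary endpoints (weeks of response, dose at first response) to > 20,000 /uL above baseline, and delete the stray question mark in the 8.3.1.1 line.
3. State which version the 18-subject interim analysis used, and record that the harmonisation was made after that look.
4. Sections 3.1 and 6.3 tie the Part 2 entry dose to the primary response criteria. Those passages must be reconciled with the single definition.

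**Cost.** Mostly wording. Compared with the literal > 20 text, slightly fewer response weeks and first responses will be counted. If the interim analysis used another version, its CR results may need to be re-derived.

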6.4. Safety

Increased Liver Chemistries

Eltrombopag administration may cause hepatotoxicity. In the ITP controlled clinical studies, one patient experienced Grade 4 (NCI Common Terminology Criteria for Adverse Events [NCI CTCAE] toxicity scale) elevations in serum liver test values during therapy with Eltrombopag, worsening of underlying cardiopulmonary disease, and death. One patient in the placebo group experienced a Grade 4 liver test abnormality. In controlled studies, elevations of ALT and indirect bilirubin were observed more frequently on the eltrombopag arm than placebo. Overall, serum liver test abnormalities (predominantly Grade 2 or less in severity) were reported in 11% and 7% of the eltrombopag and placebo groups, respectively. In the three controlled studies, four patients (1%) treated with eltrombopag and three patients in the placebo group (2%) discontinued treatment due to hepatobiliary laboratory abnormalities. Seven of the patients treated with eltrombopag in the controlled studies with hepatobiliary laboratory abnormalities were re-exposed to eltrombopag in the ITP extension study. Six of these patients again experienced liver test abnormalities (predominantly Grade 1) resulting in discontinuation of eltrombopag in one patient. In the ITP extension study, one additional patient had eltrombopag discontinued due to liver test abnormalities (all \square Grade 3). Liver chemistry stopping criteria and follow up requirements have been designed to assure subject safety and evaluate liver event etiology in alignment with the FDA Guidance for Industry – Drug-Induced Liver Injury: Premarketing Clinical Evaluation (July 2009, www.fda.gov).

Bone Marrow Reticulin Formation and Risk for Bone Marrow Fibrosis

Eltrombopag may increase the risk for the development or progression of reticulin fiber deposition within the bone marrow.

In the ITP extension study, 151 patients have had bone marrow biopsies evaluated for increased reticulin and collagen fiber deposition. Bone marrow biopsies taken after 1 year of therapy showed predominantly myelofibrosis (MF) Grade 1 or less in 140/151 (93%) of patients (Saleh et al 2013, Blood). There were 11/151 (7%) of patients with MF Grade 2. Four patients had collagen deposition reported. One patient with a pre-existing MF Grade 1 developed a MF Grade 2 and subsequently discontinued treatment with eltrombopag. Clinical studies have not yet excluded a risk of bone marrow fibrosis with clinical consequences. .

If new or worsening blood morphological abnormalities or cytopenias occur, a bone marrow biopsy should be considered, including staining for fibrosis..

Thrombotic/thromboembolic complications

Thrombotic/thromboembolic complications may result from increases in platelet counts with eltrombopag and those reported in controlled clinical studies in patients with chronic ITP included both venous and arterial events and were observed at low and normal platelet counts.

Use caution when administering eltrombopag to patients with known risk factors for thromboembolism (e.g., Factor V Leiden, ATIII deficiency, antiphospholipid syndrome, chronic liver disease). To minimize the risk for thrombotic/thromboembolic complications, do not use eltrombopag in an attempt to normalize platelet counts. Follow the dose adjustment guidelines to achieve and maintain a platelet count of $\geq 50 \times 10^9/L$ as necessary to decrease the risk for bleeding

In a placebo-controlled double-blind study (ELEVATE) of 292 patients with chronic liver disease who were undergoing an elective surgical procedure, the risk of portal venous thrombosis was increased in patients treated with 75 mg eltrombopag once daily for 2 weeks in preparation for their invasive procedure. Seven thrombotic complications (six patients) were reported within the group that received eltrombopag and three thrombotic complications were reported in the placebo group (two patients). All of the thrombotic complications reported within the eltrombopag group were of the portal venous system. Five of the six patients in the group that received eltrombopag experienced a thrombotic complication within 30 days of completing treatment with eltrombopag and at a platelet count above $200 \times 10^9/L$. Malignancy is known to increase the risk for developing a thrombotic event and four of the 6 patients either had a diagnosis or suspicion of malignancy (2 hepatocellular carcinoma; 1 possible lymphoma and 1 brain tumor).

Caution should be exercised when administering eltrombopag to patients with hepatic impairment (Child-Pugh Class A, B, C) and a lower starting dose of eltrombopag should be used in patients with any degree of hepatic impairment. Such patients should be monitored very closely. Eltrombopag is not indicated for the treatment of thrombocytopenia in patients with chronic liver disease.

The ELEVATE study was terminated in November 2009 and a Dear Health Care Professional Letter (DHCPL) was sent to all physicians enrolled in Promacta Cares in May 2010.

Hematologic Malignancies

[figure not shown]
Stimulation of the TPO receptor on the surface of hematopoietic cells by eltrombopag may increase the risk for hematologic malignancies. In the controlled clinical studies, patients were treated with eltrombopag for a maximum of 6 months. During this period no hematologic malignancies were reported in patients treated with eltrombopag. One hematologic malignancy (non-Hodgkin's lymphoma) was reported in the extension study. Eltrombopag is not indicated for the treatment of thrombocytopenia due to diseases or treatments that cause thrombocytopenia (e.g., myelodysplasia or chemotherapy) other than chronic ITP.

Cataracts

Cataracts were observed in toxicology studies of eltrombopag in rodents (see Non-clinical Information). To date, there is however, no evidence that eltrombopag increases the incidence nor progression of cataracts in patients who have received eltrombopag. In the three placebo-controlled ITP studies, 7% of patients in both the placebo and eltrombopag treatment groups had a report of cataract. A significant proportion of patients in the ITP clinical studies were also exposed to chronic corticosteroid administration.

Routine monitoring of patients for cataracts is recommended. Patients treated with eltrombopag who experience visual difficulties should have an appropriate ophthalmologic evaluation

